9.2. Screening

This research study will be explained in lay language to each potential research subject. The subject will sign an informed consent form before undergoing any screening investigations (including labs). The screening period will last for a minimum of two weeks and a maximum of six weeks.

9.3. Screening Failures

Screen failures are defined as subjects who consent to participate in the trial but are not enrolled or do not receive study drug. In order to ensure transparent reporting of screen failure subjects, to meet the Consolidated Standards of Reporting Trials (CONSORT) publishing requirements and to respond to queries from regulatory authorities, a minimal set of screen failure information will be collected and retained including demographics, screen failure details and eligibility criteria.

Subjects who are not able to achieve a clinically stable dose (as outlined in the tiered entry description), for a minimum of two weeks during the screening period will be considered screen failures. It is anticipated that for each patient enrolled, 2-3 subjects will need to be screened. Therefore, it is expected that 30-45 patients will be screened in order to enroll 15 patients.

9.4. Retesting

If the subject has signed the Informed Consent Form (ICF) and failed to meet at least one entry criterion, the site may retest laboratory values once during the screening period. Laboratory parameters can only be re-tested once. If a different laboratory parameter is found to be out of range in the re-test, no further testing is allowed and the patient will be ineligible. Re-testing may be performed to determine eligibility within the screening window. Subjects that have laboratory values that do not meet the entry criteria following the re-test are deemed a screen failure. A Quantiferon-TB® test can only be repeated once if initial is indeterminate. If second test is indeterminate or positive then the subject is considered a screen failure.

9.5. Enrollment

Women: GCA occurs more commonly in women than men (approximate 2:1 ratio) and as such it is anticipated that more women will be enrolled than men.

Pregnant women: Pregnant women are excluded from this study.

Pediatric Subjects: GCA, by classification, occurs in subjects aged ≥ 50 years of age. As such pediatric subjects are not included in this study.

Underrepresented Ethnic/Racial Minorities: GCA has been reported to occur in most ethnicities; however, it is most common in Caucasians. There will be no exclusion of any subject based on sex, ethnicity, race, or socioeconomic status.

9.6. Visit Frequency/Visit Schedule

Subjects will be evaluated for potential eligibility. Once eligibility is deemed likely, they will be consented and undergo screening. Labs pertaining to determination of eligibility will be obtained during the screening period [QuantiFERON-TB, Hepatitis panel, pregnancy test (if applicable)]. If standard of care labs (complete blood count, inflammatory markers, creatinine, transaminases) were performed at time of observed relapse these will be used for assessment of their respective eligibility laboratory parameters. If they were not drawn at time of observed relapse they will be drawn during the screening period. Standard of care labs will be obtained at each follow up visit, including the 12-week post treatment visit (W64). Lipid profiles will be obtained at week 0 and week 16.

Imaging can be performed in the study period with non-invasive angiography if clinically indicated and is

not considered a requirement for screening or necessary for study enrollment. Computed tomography angiography (CTA) and magnetic resonance angiography (MRA) is recommended at time of diagnosis for patients with GCA (level of evidence Class I, Level C) [41]. If large vessel involvement is observed on advanced imaging, follow up scan at 12-15 months is recommended.

Upon enrollment (Week 0), the study drug will be initiated and standardized GC taper begun. A follow-up visit will occur at week 4 (W4), week 8 (W8), then every 8 weeks until week 52 (W52) when study drug will be discontinued. After study drug is completed a 12-week follow up visit will occur (W64).

Visit dates can be ± 4 days from the assigned week to allow for subject travel and investigator availability. A summary of the visit schedule can be seen in the **Table 2**.

Table 2: Visit Schedule

Study Date W=Week (± 4 days)	Observed Relapse	Screening (up to 42 days)	W0	W4	W8	W16	W24	W32	W40	W52	W64
Study drug initiation			X								
Prednisone taper initiation			X								
Office visit	X		X	X	X	X	X	X	X	X	X
Data Forms											
Informed consent	X										
Eligibility review	X	X	X								
Demographics		X									
Baseline medical history		X									
Medications		X									
Tobacco use		X									
Patient Global Assessment			X	X	X	X	X	X	X	X	X
Physician Global Assessment			X	X	X	X	X	X	X	X	X
Vascular Damage Index			X							X	
Birmingham Vasculitis Activity Score			X	X	X	X	X	X	X	X	X
Imaging											
CTA or MRA Chest ^d		X									
Labs											
Hepatitis panel ^b		X*									
Tuberculosis test (Quantiferon-TB or T-spot TB)		X*									
Lipid profile			X			X					
Pregnancy test ^c		X	X	X	X	X	X	X	X	X	X
CBC w/diff	X		X	X	X	X	X	X	X	X	X
ESR	X		X	X	X	X	X	X	X	X	X
CRP	X		X	X	X	X	X	X	X	X	X
ALT	X		X	X	X	X	X	X	X	X	X
Creatinine w/EGFR	X		X	X	X	X	X	X	X	X	X
As necessary											
Hospitalization		X	X	X	X	X	X	X	X	X	X
Adverse event report		X	X	X	X	X	X	X	X	X	X
Death		X	X	X	X	X	X	X	X	X	X
Protocol deviation		X	X	X	X	X	X	X	X	X	X
Study therapy discontinuation		X	X	X	X	X	X	X	X	X	X

^a Computed tomography angiography (CTA) and magnetic resonance angiography (MRA) at physician discretion if has not had previously or at baseline of diagnosis. If large vessel involvement observed on advanced imaging, follow up scan at 12-15 months is recommended. These imaging studies are not part of protocol screening requirements and are considered standard of care (Class I, Level C) [41].

^b Hepatitis panel consists of the following: Hepatitis B surface antigen (HBsAg), anti-hepatitis B surface antibody (anti-HBs), anti-hepatitis B core antibody (anti-HBc) total, and anti-hepatitis C (anti-HCV).

^c For women of child bearing potential. Subjects of non-child bearing potential as defined in exclusion criteria are exempt from pregnancy screening.

*For patients with hepatitis panel and/or tuberculosis testing (Quantiferon-TB or T-Spot TB test) performed within 6 months prior to study entry screening for other clinical purpose, if these tests were confirmed negative and the patient has had no known exposure to either hepatitis or tuberculosis and the patient demonstrates no clinical symptomatology suggestive of these conditions then the prior negative result (within the aforementioned time frame) will be considered as their baseline negative evaluation and repeat testing for these conditions during the screening period is not required.

9.7. Screening and Critical Baseline Assessments

Cardiovascular medical history/risk factors (as detailed in the case report form) will be assessed at screening.

The following demographic parameters will be captured: year of birth, sex, and ethnicity.

Medical/medication/family history will be assessed as related to the inclusion/exclusion criteria.

9.8. Efficacy

Efficacy of baricitinib in GCA will be assessed from the presence of GCA activity including investigator assessment of signs and symptoms of GCA (new onset localized headache, scalp or temporal artery tenderness, ischemia-related vision loss [permanent vision loss due to AION, amaurosis fugax, episodic blurry vision], diplopia, or otherwise unexplained mouth or jaw pain upon mastication [i.e., jaw claudication], PMR symptoms [shoulder and/or hip girdle pain associated with inflammatory stiffness], and other features such as new or worsened extremity claudication, and fever of unknown origin), and laboratory results for serum ESR and CRP levels.

9.9. Patient's and Physician's Global Assessment of Disease Activity

The Patient's and Physician's Global Assessments of Disease Activity will be recorded on a visual analog scale (VAS). The scale for each ranges from 0 to 100 with the subject's disease activity assessment ranging from "very well" (0) to "very poor" (100). The scale for the physician's assessment ranges from "no GCA activity" (0) to "extremely active GCA" (100). The evaluating physician and subject must complete the global assessment independently of each other. The physician should preferably be the same person at every study visit for a given subject.

9.10. Pain Assessment

Subjects will be asked to assess their average pain now on a VAS ranging from "no pain" (0) to "the worst possible pain" (100).

9.11. Disease activity/damage

The Vasculitis Damage Index (VDI) will be assessed at baseline (M0) and the visit following completion of study drug (M12). The Birmingham Vasculitis Activity Score (BVAS) will be recorded at all visits including the 12-week follow up visit (M15).

9.12. Study Completion

A completed subject is one that has completed the screening period, been enrolled in the 52-week open-label enrollment period and has attended the 12-week post-treatment follow up visit. The end of the study is defined as the last subject's last visit.

10. WITHDRAWAL/STOPPING CRITERIA

10.1. Interruption of Investigational Product

In some circumstances, it may be necessary to temporarily interrupt treatment as a result of an adverse event (AEs) or abnormal laboratory values that may have an unclear relationship to investigational product. Retest timing and frequency is at the investigator's discretion.

Investigational product must be held in the following situations and may be resumed as noted in the **TABLE 3**.

Table 3. Criteria for Temporary Interruption of Investigational Product

Hold investigational product if the following laboratory test results occur:	Investigational product may be resumed when:
WBC count <2000 cells/ μ L	WBC count \geq 2500 cells/ μ L
ANC <1000 cells/ μ L	ANC \geq 1200 cells/ μ L
Lymphocyte count <500 cells/ μ L	Lymphocyte count \geq 750 cells/ μ L
Platelet count <75,000/ μ L	Platelet count \geq 100,000/ μ L
eGFR <40 mL/min/1.73 m ² (from serum creatinine)	eGFR \geq 50 mL/min/1.73 m ²
ALT* or AST >5 x ULN	ALT and AST return to <2 x ULN, and investigational product is not considered to be the cause of enzyme elevation
Hemoglobin <8 g/dL	Hemoglobin \geq 10 g/dL
Symptomatic herpes zoster	All skin lesions have crusted and are resolving
Severe infection that, in the opinion of the investigator, merits the IP being discontinued	Resolution of infection
Abbreviations: ALT = alanine aminotransferase; ANC = absolute neutrophil count; AST = aspartate aminotransferase; eGFR = estimated glomerular filtration rate; IP = investigational product; ULN = upper limit of normal; WBC = white blood cell. *ALT will be used for monitoring purposes. If abnormal then AST will be checked for further assessment of abnormalities. Alkaline phosphatase and total bilirubin will be obtained if evidence of liver disease present on ALT and/or AST to assess for need of drug interruption	

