10.2. Permanent Discontinuation of Study Drug

Any subject who is permanently discontinued from investigational product for an AE or abnormal laboratory result should have the reason for investigational product discontinuation reported as the AE or abnormal laboratory value.

Patients will discontinue study drug if the following disease related clinical events occur during the study period:

- Unprovoked venous thromboembolism (deep vein thrombosis, pulmonary embolism)
- GCA relapse occurs with objective evidence of severe ischemic event (vision loss, stroke, critical limb ischemia)
- Second GCA relapse occurs during study period

Patients will discontinue study drug following temporary interruption of the study drug if either of the following occurs.

- Study drug has been held due to a study drug-related laboratory abnormality necessitating temporary interruption (Table 3) and the laboratory abnormality that led to the investigational hold has not returned to a level at which the investigational product can be resumed (Table 3) by 4 weeks (28 days) for renal function (as determined by eGFR) or 6 weeks for the remaining laboratory parameters (42 days) from the date investigational hold commenced. For example: Example 1: a patient would be withdrawn from the study if the renal function declined due to study drug (i.e. not intercurrent illness) and the eGFR decreased to 30 mL/min/1.73m² and hold

commenced on January 1st.but the eGFR had not returned to ≥ 50 mL/min/1.73 m² by January 29th. Example 2: a patient would be withdrawn from the study if the WBC count decreased below <2000 cells/ μ L on January 1st and did not return to a value of >2500 cells/ μ L by February 11th.

- If following a study drug interruption for an identified laboratory abnormality (Table 3) the same laboratory parameter that led to study drug interruption is again affected by reinitiation of study drug. For example, platelet count prior to study drug was 150,000/uL but decreases to 50,000/uL while on the study drug. Study drug is held and the platelet count improves to 125,000/uL allowing reinitiation of study drug. Following reinitiation the platelet count decrease again to 50,000/uL.
-

In addition discontinuation of the study drug will occur if any one of the following laboratory abnormalities occur:

- ALT or AST >8 x ULN
- ALT or AST >5 x ULN for more than 2 weeks after temporary interruption of investigational product

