- ALT or AST >3 x ULN and either total bilirubin level (TBL) >2 x ULN or INR >1.5 x ULN
- ALT or AST >3 x ULN with the appearance of fatigue, nausea, vomiting, right upper-quadrant pain or tenderness, fever, rash, and/or eosinophilia ($>5\%$)
- Alkaline phosphatase (ALP) >3 x ULN
- ALP >2.5 x ULN and TBL >2 x ULN
- ALP >2.5 x ULN with the appearance of fatigue, nausea, vomiting, right upper quadrant pain or tenderness, fever, rash, and/or eosinophilia ($>5\%$).

Subjects should be discontinued from the investigational product in the following circumstances:

- WBC count <1000 cells/ μ L
- ANC <500 cells/ μ L
- Lymphocyte count <200 cells/ μ L
- Hemoglobin <6.5 g/dL

For lab values that meet permanent discontinuation thresholds, the study drug will be discontinued unless, in the opinion of the investigator, the lab abnormality is due to intercurrent illness or another identified factor. Lab tests may be repeated within 1 week to confirm whether discontinuation criteria have been met. Furthermore, if investigational product is not discontinued due to intercurrent illness, the investigator must confirm the lab value no longer meets discontinuation thresholds following the resolution of the intercurrent illness or other identified factor.

In addition, subjects will be discontinued from investigational product in the following circumstances:

- Pregnancy
- Malignancy (except for successfully treated basal cell or squamous epithelial skin cancers)

Some possible reasons that may lead to permanent discontinuation include:

- Enrollment in any other clinical trial involving an investigational product or enrollment in any other type of medical research judged not to be scientifically or medically compatible with this study
- Participation in the study needs to be stopped for medical, safety, regulatory, or other reasons consistent with applicable laws, regulations, and good clinical practice (GCP)
- Investigator Decision
 - the investigator decides that the patient should be discontinued from the study
- Subject Decision
 - the subject requests to be withdrawn from the study.

The following actions must be taken in relation to a subject that fails to attend the clinic for a required study visit.

- Site must attempt to contact the subject and re-schedule the missed visit as soon as possible

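### The three ALP stopping limits in section 10.2 need no raised ALT or AST, yet ALP and bilirubin are unscheduled and ordered by name only after an abnormal ALT and/or AST

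*Combined protocol and SAP*

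**What the plan says.** Section 10.2 introduces its list of hepatic limits with "In addition discontinuation of the study drug will occur if any one of the following laboratory abnormalities occur". The items are alternatives, so any one is enough. Three are based on ALP:

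- The first stands alone: "Alkaline phosphatase (ALP) >3 x ULN".
- The second pairs a lower ALP threshold, 2.5 times the upper limit of normal, with a total bilirubin above twice that limit.
- The third pairs the lower threshold with a clinical or blood-count sign: "ALP >2.5 x ULN with the appearance of fatigue, nausea, vomiting, right upper quadrant pain or tenderness". Raised temperature, a skin reaction or an eosinophil share above 5% also qualifies.

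The section allows drug to continue if, in the investigator's opinion, "the lab abnormality is due to intercurrent illness or another identified factor".

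The testing rules are elsewhere. The Table 3 footnote in section 10.1 sets a sequence: "ALT will be used for monitoring purposes. If abnormal then AST will be checked for further assessment of abnormalities". The remaining liver tests come last in that sequence and depend on the earlier ones: "Alkaline phosphatase and total bilirubin will be obtained if evidence of liver disease present on ALT and/or AST". The stated purpose is to judge whether drug should be interrupted. Section 9.6 spells out the standard laboratory set in the sentence that begins "If standard of care labs (complete blood count, inflammatory markers, creatinine, transaminases) were performed at time of observed relapse", and says that the set is repeated at every follow-up visit through W64. Table 2 schedules ALT at each visit from W0 to W64 and has no row for ALP, total bilirubin or AST.

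**The concern.** A stopping rule works only if the value that it depends on is measured. Here the stopping rules act on ALP regardless of transaminases, while the testing rule obtains ALP because of transaminases. A subject whose ALP rises while ALT stays normal could meet a mandatory limit without any protocol test showing it.

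Safety is the primary endpoint. Section 4 lists changes in clinical chemistry as a primary measure. Section 12.8 names hepatobiliary laboratory abnormalities as events of special interest and requires an adverse event report when they lead to interruption or discontinuation. An isolated ALP rise that is never measured can neither stop the drug nor enter that record. The investigator's freedom to attribute a value to another cause also presupposes that the value exists.

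**Working it through.** There is no stated figure to reproduce. The check compares the stopping limits with the rules for obtaining the tests.

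**Step 1: the limits.** Section 10.2 has four hepatic limits based on ALT or AST and three based on ALP: 4 + 3 = 7.

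| ALP-based limit | ALT/AST condition | Symptom or eosinophilia condition |
|---|---|---|
| ALP above 3 x ULN | none | none |
| ALP above 2.5 x ULN with bilirubin above 2 x ULN | none | none |
| ALP above 2.5 x ULN with symptoms or eosinophilia | none | yes |

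So 3 of 3 have no transaminase condition, and 2 of 3 need no clinical sign either.

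**Step 2: the schedule.** Table 2 has nine laboratory rows: hepatitis panel, tuberculosis test, lipid profile, pregnancy test, blood count with differential, ESR, CRP, ALT and creatinine. ALP or bilirubin: 0 of 9. The set in section 9.6 also omits both.

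**Step 3: visits where a result can change treatment.** Drug starts at W0 and stops at W52, and W64 is off drug. That leaves W4, W8, W16, W24, W32 and W40, which is 6 visits. Scheduled at those visits: ALT 6 of 6, ALP 0 of 6, bilirubin 0 of 6.

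**Step 4: other mentions.**
- Exclusion 12 in section 7.2 relies on a known prior bilirubin and orders no test. ALP is not an eligibility test.
- Section 12.2 refers to serum chemistry profiles and section 4 to clinical chemistry patterns. Neither names analytes or visits.
- Sections 12.8 and 12.14 order neither test.

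The Table 3 footnote is therefore the only rule that obtains ALP and bilirubin by name, and it depends on ALT and/or AST.

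**Step 5: the third limit.** The scheduled differential count can show eosinophilia, but no rule then calls for ALP.

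**Step 6: a contrast.** The limit that combines ALT or AST above 3 x ULN with raised bilirubin or INR already requires a raised transaminase, so a reflex bilirubin suits it. The ALP limits carry no such condition, so the same reflex does not suit them.

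**Secondary wording point.** Section 9.6 puts transaminases (plural) in the set for each follow-up visit. Table 2 lists ALT alone, and the footnote makes AST a reflex test.

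**The case against.** The strongest reply is that stepwise testing is a stated choice and that the ALP limits still have a use within it. The footnote sets no multiple of ULN for an abnormal ALT, so a mild rise can lead to an ALP draw, and ALP above 3 x ULN then stops drug at an ALT well below every ALT-based limit. Clinically ordered values count as well. Each visit has open-ended questioning (12.7), a brief examination that includes the liver (12.12) and a differential count, so a subject who might meet the third limit could well prompt a draw. This stands. It narrows the gap to subjects with normal transaminases and no clinically ordered draw, but does not close it: two limits are written to act without symptoms, and for the third no rule requires the test.

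A second reply is that serum chemistry profiles in section 12.2 may include ALP and bilirubin. That cannot be excluded, because the analytes are undefined. The explicit lists in 9.6 and Table 2 omit them, however, and routine ALP would make the footnote's conditional draw redundant. The redundancy argument is not conclusive alone, since the AST wording shows a similar overlap.

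A third reply is that section 6.2 lists no hepatic risk, the documents give no rate, and routine testing would bring more mandatory stop decisions. The lack of a rate stands and limits the severity. More stop decisions on measured ALP are what section 10.2 intends, and the exemption for another identified factor remains available.

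Finally, INR also appears in a 10.2 limit with no rule to obtain it. That is true. That limit requires a raised transaminase, so a reflex rule would suit it, but adding ALP and bilirubin to the schedule does not supply one.

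**Conclusion.** The concern holds. As written, three of the seven hepatic stopping limits have no protocol-specified trigger in a subject with normal transaminases, and two of the three are meant to act without symptoms. ALP and bilirubin are scheduled at 0 of the 6 visits where a result could change treatment.

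The conclusion rests on reading sections 9.6 and Table 2 as the full routine set, and on the undefined chemistry profiles in 12.2 not adding ALP and bilirubin. The number of events that could be missed is unknown and none is claimed. The point should be fixed because it concerns subject safety and the primary endpoint at small cost. Nothing here shows that the trial's overall conclusion would change.

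**What to change.** Add rows for ALP and total bilirubin to Table 2 at W0, W4, W8, W16, W24, W32, W40 and W52. The W0 value gives a reference for deciding whether a later value has another identified cause; the W52 value completes the on-treatment record. Amend the Table 3 footnote so that the two tests no longer depend on an abnormal ALT or AST. In the same edit, make section 9.6, Table 2 and the footnote agree on whether AST is routine or reflex.

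Cost: 8 visits x 15 subjects = 120 blood draws that already take place; 120 x 2 analytes = 240 extra results at most, if all 15 subjects complete the schedule. There are no extra draws. The text change is two table rows and one footnote sentence, plus the AST wording. The downside is a small laboratory cost, with some incidental abnormal values to follow up, a few of which may require a stopping decision.

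If the sponsor prefers to keep stepwise testing, section 10.2 should say that the ALP limits apply only to reflex or clinically ordered results. That makes the text consistent but leaves the detection gap.
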